5. **PHQ:** We have chosen to identify major psychopathology using the PRIME-MD Patient Health Questionnaire [74]. This questionnaire consists of nine questions that screen for depression. Each item yields a score of 0-3, and the highest possible total score for all items is 27. The scale can be used longitudinally to identify trends in depressed mood. Subjects with evidence of suicidal ideation or any other severe, acute psychiatric symptom (e.g., psychosis) will be excluded from the study. Subjects who answer “more than half the days” to 5 or more items will be excluded from the study. Since the questionnaire relies on patient self-report, all responses will be verified by the principal investigator, if a subject answers “more than half the days” to 5 or more items to confirm exclusion is warranted.
6. **Self-efficacy questionnaires:** Evaluates confidence to resist smoking across a number of different situations [60]. The scale yields a total score, as well as subscores for positive & negative affect situations, and habit/craving items. This scale has been a strong predictor of smoking outcomes in previous studies [73].
7. **Exhaled carbon monoxide measurement.** Subjects will be asked to blow into a machine that measures CO in parts per million (ppm). Levels <9 ppm are consistent with cigarette abstinence [69].
8. **Urine sample:** A urine sample will only be collected at BL, V2, V5, and V6 and analyzed only if serum can not be obtained. Urine will be tested using the NicAlert method.

The screening visit is expected to take 1.5 hours. The participant will be given a handout to record cigarette intake prior to subsequent study visits.

Study Procedures and who will perform them:

Baseline: Eligible subjects scheduled to return for a baseline (i.e. randomization) visit approximately 1 week after screening (+ 14 Days). The study nurse will review the patient's medical history and confirm current medical and pregnancy history. She will discuss each case with the study obstetrician (at the performance site) who will sign off on entry of subject into the study.

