1. **Randomization assignment:** As previously noted randomization will be 1:1 for nicotine inhaler or placebo assignment. To ensure comparability of subjects in the treatment groups, we will employ urn randomization, a probabilistic balancing procedure that assigns patients to conditions so that groups are balanced on key variables [57]. Key variables that we would like to balance groups on include history of preterm delivery (yes/no), gestational age at study entry (<19 weeks vs. \geq 19 weeks), and number of CPD (<10 vs. \geq 10).

The nurse will fax key variables for a given subject to the research pharmacist at UCONN who will enter these variables into a specially developed computer algorithm by that is

the basis for the urn randomization procedure. In this way, treatment groups will be comparable on important features that may influence treatment outcome. Once the pharmacist enters these variables, the computer assigns a treatment assignment. The pharmacist will communicate with the study nurse (by fax or e-mail) which medication box # to dispense to the subject.

2. **Maternal blood draw** (approximately 15 cc): Venipuncture will be performed using standard sterile blood drawing techniques by trained personnel. Serum will be separated on site and stored at -20 degrees C on at least a biweekly basis until transfer to UCHC where it will be stored at -70 C. Samples will be measured for cotinine, the major metabolite of nicotine, and a reliable measure of overall nicotine intake. Cotinine will be measured by GC/Mass Spectrometry at Yale University. UCHC Core Lab will ship transport tubes to Yale after subjects' Week 2 visit. If the subject does not come to Visit 2, the blood will be obtained at the next scheduled visit. Serum will also be measured for hydroxycotinine/cotinine ratio, the rate at which nicotine is metabolized. Samples will be shipped in compliance with DOT/IATA regulations (dry ice, Fed-Ex Overnight Express, etc.). The results will be emailed to the P.I. and the study coordinator at each site. Serum will measured for high sensitivity C-reactive protein (Siemens Medical Diagnostics, Los Angeles CA) by solid phase chemiluminescent immunometric assay and sICAM (R&D systems, Minneapolis, MN) measured by sandwich EIA in the GCRC core laboratory. If possible, this blood draw will be incorporated with other routine prenatal blood draws.
3. **Urine sample:** Urine will only be used as a backup for cotinine if necessary.

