self-efficacy (1) prior experience, (2) modeling or vicarious experience, (3) positive social persuasion and (4) somatic/physiological and/or emotional states [3] and specific techniques that can be used to address self efficacy in each of these domains. Multiple studies have established that the use of these techniques reliably increases self-efficacy across a variety of addictive behaviors [4].

The nurse will teach participants to use the inhaler properly (see below on instructions), and have them try it under supervision. Subjects asked to identify a quit date (within the next week), and are prepared for this quit date by the study nurse. Active inhaler or placebo dispensed with instructions to begin regular use on the quit date.

11. Dispense Study Drug/Usage Instructions: Because there is no known safe level of smoking, the goal of treatment will be total abstinence. Subjects will be informed that the nicotine inhaler is most effective if used regularly and that they should use the medication for breakthrough cravings, as needed. We will instruct subjects that each use of the inhaler should consist of puffing on it frequently up to a 20-30 minute period (as in previous studies) [66]. As a rough guide, subjects will be informed that 80 puffs on the inhaler (3-4 puffs per minute for 20-30 minutes) delivers a dose of nicotine that is approximately equal to one that would be delivered by 1 cigarette (i.e., 1 mg of nicotine). The study nurse will demonstrate for the subject the proper inhaler use.

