4. Assignment: To examine whether the blinding was successful, subjects will be asked which treatment they think they received (active or placebo inhaler).
5. Adverse Effects Inhaler & Adverse Events
6. Concomitant Medication

Nicotine Replacement for Smoking Cessation during Pregnancy

7. MNWS Questionnaire
8. Inhaler usage: We will collect used cartridges from patient and review diary of inhaler useage.
9. Counseling (10 Minutes): Counseling will focus on achieving or maintaining abstinence (set another quit date if necessary), increasing self-efficacy, skills training (depending on the patient's smoking status), and providing social support, and using inhaler to combat urges to smoke).

This visit will take 45 minutes.

Visit 4 (4 weeks after the quit date +/- 4 days). The following items will be assessed by research nurse.

1. Vital signs and weight
2. Exhaled CO measurement
3. Nicotine Use Survey
4. Questionnaires: MNWS
5. Adverse Effects Inhaler & Adverse Events
6. Concomitant Medication
7. Inhaler usage: We will collect used cartridges from patient and review diary of inhaler useage.
8. Dispensement: We will dispense a 2 week supply of study medication, if needed.
9. Counseling (10 Minutes): Counseling will focus on achieving or maintaining abstinence (set another quit date if necessary), increasing self-efficacy, skills training (depending on the patient's smoking status), and providing social support, and using inhaler to combat urges to smoke).

This visit will take 45 minutes.

Visit 5 (6 weeks after the quit date +/-10days). The following items will be assessed by research nurse.

1. Vital signs and weight
2. Exhaled CO measurement
3. Nicotine Use Survey
4. Questionnaires: MNWS, PHQ
5. Adverse Effects Inhaler & Adverse Events
6. Concomitant Medication
7. Inhaler usage: We will collect used cartridges from patient and review diary of inhaler useage.
8. Taper: (Discuss scheduled taper with goal of being off medication by 6 weeks for subjects who are abstinent from cigarette smoking (no smoking last 7 days confirmed with exhaled CO)
9. Maternal Blood draw (15cc). If possible, this blood draw will be incorporated with other routine prenatal blood draws. Will collect urine as backup.

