10. Counseling (10 Minutes): Counseling will focus on achieving or maintaining abstinence (set another quit date if necessary), increasing self-efficacy, skills training (depending on the patient's smoking status), and providing social support, and using inhaler to combat urges to smoke).
11. Serum will be sent for cotinine analysis only if the nurse identifies that the subject has significantly changed her smoking and/or inhaler use patterns (see DSMP for cotinine monitoring).

This visit will take 45 minutes.

Visit 6 (32-34 weeks gestation). The following items will be assessed by research nurse.

1. Vital signs and weight
2. Exhaled CO measurement

Nicotine Replacement for Smoking Cessation during Pregnancy

3. Nicotine Use Survey
4. Questionnaires: MNWS, PHQ
5. Adverse Effects Inhaler & Adverse Events
6. Concomitant Medication
7. Inhaler usage: We will collect used cartridges from patient and review diary of inhaler usage.
8. Maternal Blood Draw (15 cc) If possible, this blood draw will be incorporated with other routine prenatal blood draws. Will collect urine, if necessary.
9. Counseling (10 Minutes): Counseling will focus on achieving or maintaining abstinence (set another quit date if necessary), increasing self-efficacy, skills training (depending on the patient's smoking status), and providing social support, and using inhaler to combat urges to smoke).
10. Serum will be sent for cotinine analysis only if the nurse identifies that the subject has significantly changed her smoking and/or inhaler use patterns (see DSMP for cotinine monitoring).

This visit will take 45 minutes.

Birth outcomes: the research nurse or study coordinator will collect birth outcomes by chart review. Permission to conduct chart review for labor and delivery records will be included in the informed consent form. Information to be collected includes: Apgar scores, birth weight, infant sex, gestational age, head circumference, NICU admission, and infant length of stay. Other rare events associated with tobacco use during pregnancy and maternal medical conditions will also be recorded. Time to collect birth outcomes is estimated at 30 minutes.

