Aim 3: In our completed study, the effect of nicotine gum appeared to depend on cigarettes per day during the pretreatment period. For light smokers, the cessation rates were 18% and 21% for the control and nicotine groups, respectively, while for heavy smokers the rates were 0% and 15%, respectively. Since a similar effect in a sample of 150 women would provide power=0.80, using a two-sided $\alpha=0.05$, our proposed sample of 360 pregnant smokers will provide more than adequate power to detect the effect.

Aim 4: is exploratory and no sample size was calculated.

Explain on what basis it is reasonable to assume that the sample size will be obtained:

Recruitment will take place over 39 months, requiring enrollment of approximately 9 subjects per month. In our previous study, we had an on-site recruiter at each site (Baystate and Hartford Hospital) and were able to screen 3 pregnant smokers and enroll 2 subjects/week (i.e.,1 subject/site). We will also recruit from CHS in Hartford, where we expect to recruit 1 subject/month. Recruitment sites will be provided with materials designed to raise awareness of the study, including posters and brochures to be displayed prominently in all clinic areas. We will also encourage referrals from clinicians in the surrounding areas at each site, and recruit through newspapers and maternity magazines. Based on our history of recruitment, we are confident that we can reach the proposed recruitment goal.

Subject characteristics:

- Age: **at least 16 years of age**
- Ethnicity: **Hispanic and non-Hispanic. All race and ethnic groups will be eligible**
- Gender: **F**
- Other characteristics - (e.g. primary language etc.): **English or Spanish speaking**

Inclusion Criteria:

- a) smoking at least 5 CPD for the preceding 7 days
- b) previous attempt to quit smoking during pregnancy by self report
- c) 13-26 weeks gestation
- d) at least 16 years of age
- e) able to speak English or Spanish;
- f) intent to carry pregnancy to term; and
- g) stable residence

Exclusion criteria:

Nicotine Replacement for Smoking Cessation during Pregnancy

- a) current drug or alcohol abuse or dependence (other than methadone maintenance)
- b) twins or other multiple gestation
- c) unstable psychiatric disorder
- d) unstable medical problems (e.g., pre-eclampsia, threatened abortion, hyperemesis gravidarum)
- e) known congenital abnormality.

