Describe length of subject's participation in the study including number of visits, frequency of visits, and length of visits:

The subject will be in the study from the time of enrollment (13-26 weeks gestation) until 6 months after delivery. Each subject will have 10 visits. The screen and baseline visit are each 1.5 hours long. The remaining visits are approximately 45 minutes long.

Methods of Data Collection and Types of Data to be collected (may refer to attached surveys/ forms etc.)
See Attached surveys

Method(s) of data analysis:

Specific Aim 1: To compare the efficacy in pregnant smokers of the nicotine inhaler or matching placebo for smoking cessation and reduction in pregnant smokers We will first examine variation in the main outcome (7 day PPA rates at 32-34 weeks gestation) by treatment site using the intraclass correlation coefficient. If there is a difference by site, it will be used as a nesting factor in a generalized estimating equations logistic model. At the end of patient follow-up, the difference in the proportion of subjects who successfully quit smoking will be calculated along with a 95% confidence interval for the “true” difference between treatment groups. To evaluate whether randomization was effective, summary statistics for patient characteristics in the two study arms will be compared. If there is an imbalance in patient characteristics, statistical adjustment will be used to ensure that the initial results were not biased by those imbalances.

We will use a linear mixed model to evaluate the effects of the nicotine inhaler on smoking reduction or exhaled CO from baseline first to 6 weeks and then to 32 weeks gestation. Prior to these analyses, the distribution of the dependent variables, number of CPD (and exhaled CO), will be examined for normality and outliers and transformations will be performed if necessary. Treatment group and visit will be fixed factors and the intercept will be random. The model will also include a treatment-by-time interaction to test whether, over time, the number of CPD changes differentially by treatment group.

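### The primary outcome is fixed by gestation but treatment runs from the quit date, so time since quitting at the endpoint varies from about 5 to 20 weeks and the Aim 1 analysis has no term for it

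*Combined protocol and SAP*

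**What the plan says.** Two clocks run through the plan.

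- **Entry clock.** The Inclusion Criteria give "c) 13-26 weeks gestation". The section on length of participation ties this to enrolment: "The subject will be in the study from the time of enrollment (13-26 weeks gestation) until 6 months after delivery". Neither says whether the limit applies at screening or at randomization.
- **Quit-date clock.** Baseline is "approximately 1 week after screening (+ 14 Days"). At baseline: "Subjects asked to identify a quit date (within the next week"). The 6-week visit is "Visit 5 (6 weeks after the quit date +/-10days"). Study design sets 6 weeks of inhaler followed by a 6-week taper. Women not CO-confirmed abstinent at Visit 5 are taken off medication.
- **Gestation clock.** The visit list has "Visit 6 (32-34 weeks gestation"), and the primary outcome, 7-day point prevalence abstinence, is taken there. The timeline table gives 32-36 weeks for the same visit.

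Under Specific Aim 1, smoking reduction and exhaled CO are modelled "from baseline first to 6 weeks and then to 32 weeks gestation", with treatment and visit as fixed factors, a random intercept and a treatment-by-time interaction. Aim 2a reuses that model for cotinine. The urn randomization balances on "gestational age at study entry (<19 weeks vs" >=19 weeks), on preterm history and on cigarettes per day. The Aim 1 text brings in patient characteristics only if imbalance is seen.

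**The concern.** A woman entering at 13 weeks reaches the endpoint well after her course has ended. A woman entering at 26 weeks may be in the middle of it, or at her 6-week visit. One pooled difference in abstinence therefore averages over very different times since quitting, and the plan offers no way to see how much of it comes from women still inside the course. Cotinine is affected more directly: it measures nicotine from any source, including the inhaler, so the comparison at 32-34 weeks in Hypothesis 2a depends on how many women are still using the product. The plan also treats the 6-week and late-pregnancy assessments as two steps, without saying what happens when they fall together. The postpartum follow-up fills little of this gap, since Visit 7 is by telephone without CO and Visit 8 takes CO only if the visit is attended.

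**Working it through.** **The plan's own figure.** An odds ratio of 2.1 on 14.9% gives 26.9%. With 180 per arm and two-sided alpha 0.05, power is 0.802, so the stated 0.80 is reproduced. The plan gives no figure for how many women are on drug at the endpoint.

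**Inputs.** Entry at E = 13 to 26 weeks. The lag L from entry to quit date is 1-3 weeks to baseline plus 0-1 week to the quit date: nominally 1-2 weeks, at most 4. Visit 5 = E + L + 6 (+/- 10 days, 1.4 weeks). Course end = E + L + 12.

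**Time since quit date at the endpoint, L = 1.**
- Earliest entrant seen at 34 weeks: 34 - (13 + 1) = 20 weeks.
- Latest entrant seen at 32 weeks: 32 - (26 + 1) = 5 weeks.

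**Latest entrant, E = 26.**

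| L (weeks) | Quit date | Visit 5 | Course end |
|---|---|---|---|
| 1 | 27 | 33 | 39 |
| 2 | 28 | 34 | 40 |
| 4 | 30 | 36 | 42 |

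On nominal lags Visit 5 lies inside the 32-34 week window. It goes beyond the window only with a delayed baseline or a late visit, both of which the visit windows permit.

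**Share with nominal Visit 5 at 32 weeks or later.** This needs E >= 26 - L. With entry uniform on 13-26 weeks (assumption): L = 1 gives 1/13 = 8%; L = 2 gives 2/13 = 15%.

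**Share within 12 weeks of the quit date at gestation G.** This needs E > G - 12 - L.

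| G | L = 1 | L = 2 |
|---|---|---|
| 32 | 7/13 = 54% | 8/13 = 62% |
| 33 | 6/13 = 46% | 7/13 = 54% |
| 34 | 5/13 = 38% | 6/13 = 46% |
| 36 | 3/13 = 23% | 4/13 = 31% |

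**Sensitivity to the entry distribution, G = 33, L = 1-2.**
- Linear skew to early entry (mean 17.3 weeks): (6/13)^2 to (7/13)^2 = 21-29%.
- Linear skew to late entry (mean 21.7 weeks): 1 - (7/13)^2 to 1 - (6/13)^2 = 71-79%.
- Steeper early skew (mean about 16.2 weeks): (6/13)^3 to (7/13)^3 = 10-16%.

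**Sensitivity to delay.** A mean lag of 2.5 weeks with uniform entry gives 2.5/13 = 19% with Visit 5 at 32 weeks or later, and 7.5/13 = 58% within 12 weeks at G = 33. If 26 weeks is also read as running up to 27, these become 3.5/14 = 25% and 8.5/14 = 61%.

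**Share still assigned drug at 33 weeks.** Only Visit 5 quitters continue, so the share is f6 + q x (f12 - f6). Here f6 and f12 are the shares within 6 and 12 weeks of the quit date, and q is the 6-week quit rate.
- L = 1: f6 = 0, f12 = 6/13. With q = 9.6% (placebo, prior gum trial) the share is 4%; with q = 26.9% it is 12%.
- L = 2: f6 = 1/13, f12 = 7/13. With q = 15% (assumed) the share is 15%; with q = 26.9% it is 20%.

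The range is therefore about 4-20% of all women. Among abstainers, the 46-54% applies if quitting does not depend on entry time.

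**What the urn cut offers.** 19 + about 2 + 12 = 33 weeks, so the cut falls close to the point where the course ends at the endpoint. With uniform entry the strata hold about 180 x 6/13 = 83 and 180 x 7/13 = 97 women per arm. Power for 14.9% vs 26.9% is then 0.48 and 0.54, and the 95% half-width is about 12 and 11 percentage points, against 8 for the full sample.

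**The case against.** The strongest reply is that the endpoint is tied to gestation on purpose. Hypothesis 1 is about abstinence at 32-34 weeks because late-pregnancy smoking is what bears on birth weight. It makes no claim about persistence off drug, and the 14.9% planning rate comes from a trial with the same endpoint and a 6-plus-6-week course. That stands: an off-drug effect is a different question, and its absence is not an error.

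Several stronger readings are tempting and are not supported.

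- **That half of all women are on drug at the endpoint.** The figure near one half is calendar time, or at most a statement about abstainers. It rests on an assumed entry distribution and leaves out the stop for non-quitters at Visit 5. Dispensing is scheduled only at baseline, Visit 2 and Visit 4, so actual use during the taper cannot be worked out from the documents.
- **That the arms are compared unfairly.** Timing is the same in both arms, the urn balances entry gestation, and exhaled CO does not measure nicotine.
- **That the mixed models are invalid for late entrants.** Visit as a categorical factor with a random intercept imposes no order or spacing on Visits 5 and 6. The weakness is that the contrast is hard to interpret.
- **That Visit 5 commonly follows the endpoint window.** This needs delays, and hardly arises under the 32-36 week window in the timeline table.

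It is also fair to say that splitting at 19 weeks does not cleanly separate on-drug from off-drug abstinence. Each stratum mixes women stopped at Visit 5 with women who continued, and entry gestation may itself affect quitting.

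**Conclusion.** The concern holds as a matter of interpretation and precision. Time since quit date at the primary endpoint varies about fourfold, from about 5 to 20 weeks, and the Aim 1 analysis neither adjusts for it nor displays it. For entrants at about 24-26 weeks the 6-week visit and the endpoint visit coincide, and the documents do not say how that is handled. The percentages (8-15% with overlap; 46-54% within 12 calendar weeks) depend on uniform entry and a 1-2 week lag. The direction does not: any spread of entry across 13-26 weeks produces the mixture. The planned sample size and the validity of the randomized comparison are untouched. The change is worth making because entry gestation is already a balancing factor, which the plan would adjust for only if imbalance appeared.

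**What to change.** Leave eligibility, sample size and endpoint as they are, and add the following to the analysis text.

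1. Adjust the primary comparison for the urn factors, including entry gestation <19 vs >=19 weeks, whether or not imbalance is seen. Express the result as a difference in proportions with its 95% confidence interval, so that it matches the measure the plan already reports.
2. Report that difference descriptively within the two entry-gestation strata, stating the low precision and that the split does not isolate on-drug from off-drug abstinence.
3. Tabulate inhaler use at Visit 6 by arm; it is already collected.
4. As a sensitivity analysis of the cigarettes-per-day, CO and cotinine models, replace visit by weeks since the first quit date. Naming the first date matters because counselling at Visits 2 to 6 allows another to be set.

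Three points in the protocol must be reconciled: the Visit 5 and Visit 6 passages for women in whom the two overlap, including the medication decision tied to Visit 5; the 32-34 and 32-36 week windows for Visit 6; and whether 13-26 weeks applies at screening or at randomization.

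The cost is analysis wording, one or two tables and one extra model per outcome, all from data already planned.
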